5.1. General Considerations

- The primary analysis will be performed after the database is locked and randomization schedule is released.
- Participants will receive treatment at the outset of the study (treatment group) or have treatment delayed until Week 24 (control group). The delayed treatment for control group is optional and referred to as "Optional Treatment".
- Control Period (CP), Treated Period (TP) are defined in Table 5-1.

Table 5-1 **CP and TP definition**

| Randomization | Period | Treatment | Start Date | End Date |
|---------------|--------|------------------------|---------------------------------|---|
| Group | | Group Label | | |
| Treatment | СР | VOLUMA | Initial treatment date | The date of effective assessment for Week 24. If multiple assessments fall into Week 24 window, the date of the assessment included in the Week 24 analysis will be used as end date. For participants who exit before Week 24, the end date is study exit date. For participants with intermittent missing assessment at Week 24, the target day for Week 24 (Day 169) will be the end day. |
| | TP | VOLUMA | Initial treatment date | Study exit date |
| Control | СР | Control | Randomization date | For participants who do not receive optional treatment If multiple assessments fall into Week 24 window, the date of the assessment included in the Week 24 analysis will be used as end date. For participants who exit before Week 24, the end date is study exit date. For participants with intermittent missing assessment at Week 24, the target day for Week 24 (Day 169) will be the end day. For participants who receive optional treatment: The day before optional treatment |
| | ТР | VOLUMA Post-Control | Optional initial treatment date | Study exit date |

JUVÉDERM® VOLUMA® with Lidocaine

- For CP, effectiveness analyses and baseline characteristics will be performed on the mITT population using the "as-randomized" assignment. One of the sensitivity analyses for the primary endpoint will be based on PP population. Safety analyses for CP will be conducted using the Safety Population based on "as-treated" assignment.
- For TP, effectiveness and safety summaries will be performed on the VITP and VOTP using "as-treated" assignment.
- For applicable effectiveness endpoints, baseline is defined as the last non-missing value prior to the start of study treatment for treatment group or no later than randomization date for control group.
- Descriptive statistics for continuous variables include the sample size (n), mean, standard deviation, median, 1st and 3rd quartiles, minimum, and maximum.
- Summary statistics for categorical variables include the sample size (N1), frequency count, and percentage.
- Partial dates will be treated as missing in computations but listed in the data listings as they appear on the eCRFs unless otherwise specified. No imputation of missing values will be performed, unless otherwise specified.
- The level of significance used for all statistical tests will be 0.05, 2-sided, unless stated otherwise.
- The change from baseline values will be computed as the value for the post baseline visit minus the baseline value, unless otherwise indicated.
- All statistical analysis will be performed using SAS version 9.3 or higher.
- MedDRA will be used to code adverse events and medical history.
- WHO Drug Dictionary will be used to code medications.

5.2. Participant Dispositions

The number of participants in each of the 5 study populations (mITT, PP, Safety, VITP and VOTP) will be summarized (by treatment group as appropriate).

The number of participants screened will be summarized. Screen-failure participants (ie, participants who are screened but are not randomized) and the associated reasons for failure as recorded in the eCRF will be listed for the all screened participants.

Summary of study disposition will be provided by treatment group for the following:

- Number of participants randomized
- Number of participants treated as randomized
- Number of participants treated not as randomized

For mITT Population during Control Period

- Number of participants completed Control Period
- Number of participants discontinued during Control Period
- Reasons for discontinuation during Control Period

JUVÉDERM® VOLUMA® with Lidocaine

For VITP during Post-Control Period

- Number of participants continued after Control Period
- Number of participants completed Post-Control Period
- Number of participants discontinued during Post-Control Period
- Reasons for discontinuation during Post-Control Period

For VOTP during Post-Control Period

- Number of participants continued after Control Period
- Number of participants completed Post-Control Period
- Number of participants discontinued during Post-Control Period
- Reasons for discontinuation during Post-Control Period

For mITT Population during the study

- Number of participants completed the study
- Number of participants discontinued from the study
- Reasons for discontinuation from the study

5.3. Primary Effectiveness Endpoint Analysis

5.3.1. Definition of Endpoint

The primary effectiveness endpoint is the change from baseline in mean change in the nose volume based on 3D imaging at Week 24, which is calculated by digital analysis of each participant's 3D images. The change from baseline in nose volume is also referred to as nose volume change.

5.3.2. Main Analytical Approach

The hypotheses described in Section 2 will be tested based on the mITT population using MMRM model. The model will include nose volume change as the response variable, and treatment, timepoint (visit of Weeks 8, 16, and 24), treatment-by-timepoint interaction as fixed effect. Participant will be included in the model as a random effect. Restricted maximum likelihood method will be used. The within-participant correlation will be modeled using the unstructured covariance matrix. If the model does not converge, then the Toeplitz covariance structure will be used. If the model with the Toeplitz covariance structure does not converge, then other methods will be further explored and used. The Kenward-Roger approximation (Kenward 1997) will be used to estimate denominator degrees of freedom. In this MMRM model, missing at random will be assumed, therefore no imputation will be conducted.

Each treatment effect and treatment comparisons will be estimated by the LS Means and their differences in LS Means, along with their SE and 95% CIs, and the p-value corresponding to the between-treatment group difference.

The sample SAS code is given as follows

proc mixed data = effectiveness_dataset METHOD=REML;
 class trt visit subjid;
 model chg = trt visit trt*visit / s ddfm= kr;
 Repeated visit / type = UN subject = subjid;
 lsmestimate trt*visit;
 run;

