6.2.2 Control Period

6.2.2.1 Randomization Visit – All Subjects

Before randomization, female subjects of childbearing potential (sexually active and not sterile, surgically sterilized, or postmenopausal for at least 1 year) must have a negative urine pregnancy test confirmed on the day of randomization, if the screening pregnancy test was not performed within 7 days of the day of randomization.

All eligible subjects will be randomized at a 3:1 ratio either to receive VOLUMA with Lidocaine treatment at the outset of the study (ie, treatment group) or to be followed in a 24-week “no-treatment” observation period followed by an optional delayed treatment (ie, control group).

Before randomization, 3D digital images of the nose area must be captured for all eligible subjects, which will be used as baseline data for subsequent calculation of the nose volume change and nose aesthetic improvement including dorsal height, dorsal width, nasofrontal angle, nasolabial angle, nasal root height, nasal length, and ala depth. These 3D images must be captured before receiving treatment (treatment group subjects). 3D photos need not be repeated before treatment if study treatment is not administered at the randomization visit. The procedures to be performed during the randomization visit are specified in [Table 2](#).

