9.1.3 Treatment Regimen Adjustments

Up to 2 treatment sessions (initial and touch-up) approximately 8 weeks apart are allowed. The TI will determine the appropriate volume of VOLUMA with Lidocaine to inject at the initial and touch-up treatments based on his/her clinical experience and the randomization assignment, but the minimal volume must exceed 0.5 mL and maximum volume is not to exceed 3.0 mL for initial and touch-up treatments combined.

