| JUVI | DEKIM | VOLC | IVIA WIL | II LIUOCAIIIC | |
|------|--------|--------|------------|----------------------------------|----|
| | | 6.3.3. | Protocol | Deviations | 25 |
| | | 6.3.4. | Medical | History | 26 |
| | | 6.3.5. | Prior/Co | ncomitant Medications | 26 |
| | | | | | |
| | | | | | |
| | | | | | |
| | | | | | |
| | | | | | |
| | | | | | |
| | 6.4. | Data H | Iandling C | Convention | 28 |
| | | | _ | Window | |
| | | | | Effectiveness | |
| | | | 6.4.1.2. | Safety | 29 |
| | | 6.4.2. | | Date Imputation | |
| | | | | Missing/Incomplete AE Start Date | |
| | | | | Missing/Incomplete AE End Date | |
| 7. | Refere | nces | | | 31 |
| | | | | | |

List of Tables

| Table 4–1 | Analysis Populations | 12 |
|-----------|--|----|
| Table 5-1 | CP and TP definition | 13 |
| Table 5–2 | Sensitivity Analyses of Primary endpoint. | 16 |
| Table 5–3 | Secondary Effectiveness Analyses | 17 |
| | | |
| Table 5–5 | Exposure to Study Treatment. | 19 |
| Table 5–6 | Administration of Study Treatment | 19 |
| Table 5-7 | TEAE Summaries | 20 |
| Table 5-8 | ISR Analyses | 21 |
| Table 5-9 | Procedural Pain Analyses | 21 |
| Table 6-1 | Protocol Deviation Summary | 26 |
| Table 6-2 | Prior and Concomitant Medications | 26 |
| Table 6-3 | Effectiveness Analysis Visit Definitions for Treatment Group during Control Period and Treated Period. | 29 |
| Table 6-4 | Effectiveness Analysis Visit Definitions for Control Group during Control Per | |
| Table 6-5 | Effectiveness Analysis Visit Definitions for Control Group during Treated Per | |
| Table 6-6 | Imputation Scenarios | 30 |

SAP Version History

This SAP for study 1894-701-008 is based on the protocol Amendment 1 (dated 22-Sep-2017).

| | SAP Version History Summary | | | | | |
|----------------|-----------------------------|---|---|--|--|--|
| SAP Version | Approval Date | Change | Rationale | | | |
| 1 | August 13, 2019 | Not Applicable | Original version | | | |
| 2 | | Baseline definition for efficacy analysis in control group | Including participants with baseline 3D photos taken after randomization due to Canfield setting-up error | | | |
| | | Add a rule of analysis for participants who have two measurements at one visit in Section 6.4.1 | Dealing with data issues: some participants have more than one photo taken at one visit | | | |
| | | Add explanation of analysis population definition change | Providing justification of the changes | | | |

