A sample size of 90 treatment and 30 control participants will provide 99.6% power to detect a difference of 0.9 mL in the mean volume change from baseline between the treatment and control group, assuming a mean change from baseline of 1.1 mL with standard deviation of 0.9 mL, and mean change from baseline of 0.2 mL with standard deviation of 0.9 mL, for the treatment and control groups, respectively. This calculation is based on a 2-sample, 2-sided t-test at 5% significance level. The assumptions of means and standard deviations are estimated from Allergan studies VOLXC-AP-ND-001 and VOLUMA-004. In order to have over 100 treatment group participants complete 1-year follow-up, accounting for participant attrition of 15% during the whole study duration through Week 48, at least 120 participants in the treatment group and 40 participants in the control group will be randomized.

4. Populations for Analysis

The analysis populations will consist of participants as defined in Table 4–1:

Table 4–1 Analysis Populations

| Population | Definition | Study Treatment | |
|---|--|--------------------|--|
| mITT Population | mITT Population All participants who are randomized and have at least 1 assessment of change from baseline in nose volume | | |
| PP Population | All mITT participants who have baseline and Week 24 assessments of | | |
| Safety Population | All randomized participants who receive VOLUMA treatment in the Control Period or who do not receive VOLUMA treatment in the Control Period and with at least 1 follow-up assessment | As treated | |
| VOLUMA Initial Treated Population (VITP) | Participants randomized and received VOLUMA treatment in the Control Period with up to 48 weeks follow-up | As treated | |
| VOLUMA Optionally Treated Population (VOTP) | Participants randomized to control group and received optional VOLUMA treatment in Post-Control Period. These participants will have up to 24 weeks follow-up after optional VOLUMA treatment (or touch-up treatment). | As treated | |

JUVÉDERM® VOLUMA® with Lidocaine

5. Statistical Analyses

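### Adding baseline nose volume to the primary MMRM would be a near-free gain in precision; the pooled covariance matrix needs only named sensitivity analyses

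*SAP*

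**What the plan says.** SAP 2 and 5.3.2 give the same three fixed effects for the primary model: treatment, visit and their interaction. The sample code reads "model chg = trt visit trt*visit / s ddfm= kr" and "Repeated visit / type = UN subject = subjid". There is no baseline term, and one unstructured matrix serves both arms.

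The plan nevertheless collects and uses a baseline. Protocol 6.2.2.1 states: "Before randomization, 3D digital images of the nose area must be captured for all eligible subjects". SAP 5.1 adds, as a general convention that applies unless otherwise indicated: "The change from baseline values will be computed as the value for the post baseline visit minus the baseline value".

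Allocation is 3:1. The sample size section (SAP 3) assumes an SD of 0.9 mL in the treatment arm and, for controls, a "mean change from baseline of 0.2 mL with standard deviation of 0.9 mL". Protocol 9.1.3 leaves the injected amount to judgement: "The TI will determine the appropriate volume of VOLUMA with Lidocaine to inject".

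The sensitivity analyses in SAP Table 5-2 are the same MMRM on the per-protocol population, a 2-sample t-test with no variance form stated, and a Wilcoxon test. None adjusts for baseline, and none is stated to let the variances differ by arm.

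**The concern.** A pre-treatment measurement of the outcome is usually the first covariate considered in a model for change. Here it comes from an image already required of everyone, so it needs no new data. Without it, any variation in change that baseline could explain stays in the residual and widens the interval for the treatment difference. That interval is what the trial will report as the size of the effect.

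A second, smaller question arises in the same code. When one arm is three times the other, a standard error from a pooled variance is right only if the arms have the same spread. Only treated noses receive individually chosen volumes, so a different spread is plausible. No planned analysis is specified to show whether it matters.

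**Working it through.** **Plan's own figure.** 90 versus 30 participants, difference 0.9 mL, SD 0.9 mL in both arms, 2-sided 5% (SAP 3). The normal approximation gives 99.73% power, the pooled t-test (118 df) 99.70% and the separate-variance t-test (49.8 df) 99.64%. The stated 99.6% is reproduced.

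**Numbers analysed.** 120 and 40 randomized with 15% attrition: 120 × 0.85 = 102 and 40 × 0.85 = 34. The plan states the 15% through Week 48, so this is cautious for Week 24.

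**Unadjusted reference.** With complete data, the Week 24 contrast from the planned MMRM equals the pooled t-test.

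- SE = 0.9 × √(1/102 + 1/34) = 0.178 mL.
- 95% CI width = 2 × 1.978 × 0.178 = 0.705 mL.
- Power for 0.9 mL is 99.89%.
- With all 120 and 40 analysed, the width would be 2 × 0.3245 = 0.649 mL.

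**Adding baseline.** With complete data, the Week 24 contrast with baseline and baseline-by-visit is an analysis of covariance on 133 df. Let r be the correlation of baseline with change; the documents do not give it, so a range is assumed.

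SE = 0.9 × √[(1 − r²) × (1/102 + 1/34) × (1 + 1/132)]

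The last factor is the average price of estimating one slope.

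| r (assumed) | residual variance | SE, mL | CI width, mL | change from 0.705 |
|---|---|---|---|---|
| 0 | unchanged | 0.179 | 0.708 | +0.4% |
| 0.1 | 1% lower | 0.178 | 0.704 | −0.1% |
| 0.3 | 9% lower | 0.171 | 0.675 | −4% |
| 0.5 | 25% lower | 0.155 | 0.613 | −13% |

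Break-even is where (1 − r²)(1 + 1/132) = 1. Then r² = 1/133 and r is about 0.09. Only r² enters, so the sign of the correlation does not matter.

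**Pooling over arms.** Treated SD is held at 0.9 mL; control SDs other than 0.9 are assumptions.

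- Pooled SE = √[(101·sT² + 33·sC²)/134] × √(1/102 + 1/34)
- True SE = √(sT²/102 + sC²/34)

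For control SD 0.75, the pooled SE is √(100.37/134) × 0.198 = 0.171 and the true SE is √(0.00794 + 0.01654) = 0.156. Error rates and mean CI widths come from simulation of the Week 24 comparison (4,000,000 replicates).

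| control SD, mL | pooled SE | true SE | pooled SE is | pooled type I error | mean CI width, pooled / by arm |
|---|---|---|---|---|---|
| 0.9 (plan) | 0.178 | 0.178 | correct | 5.0% | 0.704 / 0.711 |
| 0.85 | 0.176 | 0.171 | 3% too large | 4.4% | 0.694 / 0.681 |
| 0.75 | 0.171 | 0.156 | 10% too large | 3.2% | 0.677 / 0.622 |
| 1.2 | 0.195 | 0.224 | 13% too small | 8.9% | 0.768 / 0.898 |

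The separate-variance test held 5.0% throughout. Power for 0.9 mL was at least 97% in every row with either method. The SE ratios are the same at 120 versus 40.

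**The case against.** The strongest objection is that nothing in the trial's conclusion is at stake. Power is above 99% under the plan's assumptions, omitting baseline does not bias a randomized comparison, and an MMRM on change with an unstructured matrix is a coherent prespecified analysis. All of that stands. The remaining case is about precision only.

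The second objection is that an absolute baseline nose volume may not exist as a variable. Protocol 7.1.1 and SAP 5.3.1 describe the outcome as a volume change from digital image analysis, and the subtraction rule in SAP 5.1 is a general convention. This also stands in part: a baseline value is implied, not confirmed, so the fix must start by confirming it. The correlation is equally unknown and the gain could be negligible. The documents support a very small cost, not a particular benefit.

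Three stronger readings are tempting:

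- A reader might infer that pooling inflates type I error, so that by-arm matrices must be primary. The only SDs given are 0.9 and 0.9 mL, at which there is no distortion. Inflation requires controls to vary more than treated participants, which is the less likely direction. If treated participants vary more, the test is conservative.
- A reader might treat the unnamed last resort after the Toeplitz structure as a material defect. It is a missing detail that is unlikely to be needed.
- A reader who sets the version history ("Including participants with baseline 3D photos taken after randomization due to Canfield setting-up error") against the SAP 5.1 definition ("or no later than randomization date for control group") might conclude that the covariate is undefined for some controls. Which photograph counts as baseline is a separate question. A version history entry that differs from current text is not in itself an error, and the covariate proposed here is whatever value the change score already uses.

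**Conclusion.** The primary model leaves out a covariate that the plan appears to have already. Adding it costs about 0.4% in CI width if baseline is unrelated to change, breaks even at a correlation of about 0.09, and narrows the interval by about 4% at 0.3 and 13% at 0.5. These figures assume 102 versus 34 participants, SD 0.9 mL, complete data at Week 24, a linear relation and the stated correlations. The omission does not invalidate the planned analysis, and the finding of efficacy does not depend on it.

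The pooled matrix agrees with the planning assumption and need not be replaced. Because allocation is 3:1 and the SDs could differ, the report should show how far the interval moves without pooling: 10% too large an SE at an assumed control SD of 0.75 mL, 13% too small at 1.2 mL.

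**What to change.** Before the randomization schedule is released:

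1. Confirm that the imaging system returns an absolute baseline nose volume.
2. In SAP 2 and 5.3.2, add baseline nose volume and baseline-by-visit as fixed effects. State that baseline is the same value that is subtracted to form the change. Code: `model chg = base trt visit trt*visit base*visit / s ddfm=kr;`
3. If only a volume difference is returned, name in advance one baseline 3D measure from the same image, for example dorsal height, and use it as `base`.
4. Keep the pooled unstructured matrix as primary. Add two rows to Table 5-2: the same model with the unstructured matrix estimated by arm (`group=trt` on the REPEATED statement), and a Week 24 t-test with Satterthwaite degrees of freedom.
5. Record the change, its date and the reason in SAP Appendix 2.

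The cost is a few lines of text and code and three more fixed-effect parameters. If the volume is used, no participant is lost, because anyone with a change score has a baseline value. It would be a second change to the primary analysis after the move from t-test to MMRM, which is why the date matters. The by-arm sensitivity model adds six covariance parameters, with the control matrix resting on about 34 to 40 participants. With equal SDs its interval is about 1% wider (0.711 against 0.704 mL). With baseline included, it converged in 3,000 of 3,000 simulated fits with 15% dropout and assumed visit correlations of 0.7 to 0.8, though with a purpose-written REML optimizer, not PROC MIXED.

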5.3.3. Sensitivity Analyses

In addition, sensitivity analysis of the primary effectiveness endpoint will be done using MMRM based on PP population. The analysis model is the same for the primary analysis. Listing of the participants with effectiveness data excluded PP analysis will be provided for mITT population.

Additional sensitive analyses include using t-test and Wilcoxon rank test for group comparison using observed data based on mITT population.

Summary of sensitivity analyses are presented in Table 5–2.

Table 5–2 Sensitivity Analyses of Primary endpoint

| Endpoint | Description | Timing | Methodology |
|---|--|------------------------|-----------------|
| | Superiority of the treatment group over control group (PP population) | Weeks 8, 16, and 24 | MMRM |
| Nose volume change based on 3D digital imaging (sensitivity analyses) | Superiority of the treatment group over control group using observed data (mITT population) | Week 24 | 2-sample t-test |
| (sensitivity analyses) | Superiority of the treatment group over control group using observed data (mITT population) This analysis will be done when normality is not established | Week 24 | Wilcoxon test |

5.3.4. Supplementary Analyses

Descriptive statistics will be summarized for VITP and VOTP, which includes all visits after study injection (i.e., Weeks 8, 16, 24, 36, and 48 for the former and Weeks 8, 16, and 24 for latter).

JUVÉDERM® VOLUMA® with Lidocaine

5.4. Secondary Effectiveness Endpoints Analysis

5.4.1. Secondary Effectiveness Endpoints

The secondary effectiveness endpoints are the proportion of GAIS responders by EI at Week 24, the proportion of GAIS responders by participant at Week 24, and the proportion of NSS responders by participant at Week 24.

A GAIS responder is defined as a participant with "Improved [1]" or "Much improved [2]" marked on the 5-point GAIS (Much Improved [2], Improved [1], No Change [0], Worse [-1], Much Worse [-2]) as assessed by EI or participant at Week 24.

An NSS responder is a participant with "Satisfied [1]" or "Very Satisfied [2]" marked on the 5-point NSS (Very satisfied [2], Satisfied [1], Neutral [0], Dissatisfied [-1], Very dissatisfied [-2]) at Week 24.

